6.2.1 Oral Administration of dmLT

Participants will have nothing to eat or drink for 90 minutes before and after dosing. For oral routes of administration, the sodium bicarbonate buffer solution (2 g sodium bicarbonate in 150 mL of sterile WFI) is split into a 120 mL and 30 mL aliquot (e.g., into two disposable drinking cups). The designated amount of dmLT is transferred from the working dilution, as specified, into 30 mL of sodium bicarbonate buffer solution. Once the dmLT is added to the sodium bicarbonate buffer solution it must be administered within 15 minutes to the study participant. For oral vaccination, participants first ingest 120 mL of sodium bicarbonate buffer and then within 1-5 minutes ingest the designated dosage of dmLT, suspended in 30 mL sodium bicarbonate buffer solution. For the oral cohorts, participants that vomit or spit out study product within 90 minutes of taking the study product will be replaced.

6.2.2 Oral Administration of Placebo (Sodium Bicarbonate Buffer alone)

Participants will have nothing to eat or drink for 90 minutes before and after dosing. As with active vaccination, a sodium bicarbonate buffer solution will be prepared (2 g sodium bicarbonate in 150 mL of sterile WFI) and maintained at room temperature until use. To maintain the blind, participants first ingest 120 mL of the sodium bicarbonate buffer and then within 1-5 minutes ingest the remaining 30 mL of sodium bicarbonate buffer solution. For the oral cohorts, participants that vomit or spit out study product within 90 minutes of taking the study product will be replaced.

6.2.3 Sublingual Administration of dmLT

For SL routes of administration, participants will have nothing to eat or drink for 30 minutes before and after dosing. Participants will be asked to gargle and rinse their mouths for 10 ± 5 minutes with bottled water or treated tap water that is supplied by study staff. After this is completed, a sterile gauze will be placed under the participant's tongue for ~ 1 minute ± 15 seconds. Afterwards, the gauze will be removed, and the participant will receive the sublingual vaccine immediately. The designated amount of vaccine will be given in a 100 μ L (0.1 mL) volume, diluted with normal saline, and be delivered underneath the tongue using a calibrated tuberculin or insulin syringe (or equivalent). After delivery of vaccine, participants will be instructed to tilt their head forward, chin to chest, for at least 1 minute. Afterwards, participants will be instructed to bring their head to normal position and swallow. Participants will be reminded not to eat, drink, or rinse the mouth for 30 minutes following dosing. For the SL cohorts, participants that vomit or spit out study product within 30 minutes of taking the study product will be replaced.

6.2.4 Sublingual Administration of Placebo (Normal Saline)

For SL routes of administration, participants will have nothing to eat or drink for 30 minutes before and after dosing. To maintain the blind, participants will undergo the same procedure as described above in [Section 6.2.3](#) for the active SL vaccination, except 100 μ L (0.1mL) of normal saline will be delivered under the tongue instead of active study product. For the SL cohorts, participants that vomit or spit out study product within 30 minutes of taking the study product will be replaced

6.2.5 Intradermal Administration of dmLT

For intradermal routes of administration, the arms of the participant will be examined for the most appropriate injection site, considering the avoidance of scars, tattoos, marks, etc. which may obscure or make the evaluation of local site reactogenicity difficult. Subsequent doses of vaccine, may be administered in the same arm or the arm may be switched as preferred by the participant. The designated amount of vaccine will be delivered in a single 100 μ L (0.1 mL) volume by the ID route, using a tuberculin syringe (or equivalent) with a single-use sterile 25 gauge (or smaller) needle.

6.2.6 Intradermal Administration of Placebo (Normal Saline)

To maintain the blind, participants will have the same procedure as described above in [Section 6.2.5](#) for the active ID vaccination, except 100 μ L (0.1 mL) of normal sterile saline will be administered by the ID route instead of active study product.

6.3 Modification of Study Intervention/Investigational Product for a Participant

Not applicable

6.4 Accountability Procedures for the Study Intervention/Investigational Product(s)

The site principal investigator is responsible for ensuring study product distribution and disposition and has ultimate responsibility for study product accountability. The Investigator may delegate to the Site Research Pharmacist responsibility for study product accountability. Study product accountability records should include date received, date prepared, date administered, time of preparation, quantity administered, and the subject identification number to whom the study product was administered. The designated research pharmacist(s) will be responsible for maintaining accurate records of the shipments and dispensing the investigational products. The

pharmacy records must be available for inspection by the DMID monitor and is subject to inspection by a regulatory agency (e.g. FDA) at any time. Aliquots of dmLT dilutions in saline prepared for each cohort dosing level should be saved and stored at $-80^{\circ}\text{C} \pm 15^{\circ}\text{C}$ for later shipment to PATH's analytical laboratory subcontractor for dmLT dose verification (see MOP for details on shipping instructions). Temporary storage on dry ice for up to 24 hours is allowed. The dose verification frozen aliquots may be stored as a reagent (i.e., does not need to be stored under the conditions of an investigational product). Used and unused study product (dmLT vials) will be retained and monitored until written authorization from the Study Sponsor (CPM/DMID) for destruction of study products is obtained. Final disposition of the unused study products will be determined by DMID and communicated to the participating sites by the DMID Clinical Project Manager.

6.5 Assessment of Subject Compliance with Study Intervention/Investigational Product

Participants will be vaccinated and observed for the respective time following dosing by a blinded member of the study team who is licensed to administer medications or vaccines. Observation times are approximately 90 minutes following oral dosing and 30 minutes following SL and ID dosing.

There will be no fasting requirement for the 30 minute observation period following ID dosing.

6.6 Concomitant Medications/Treatments

Participants are permitted to take birth control pills and vitamins throughout the course of the study; herbal supplements are not permitted. In addition, participants will be instructed that prescription or OTC anti-inflammatory medications will not be permitted in the 48 hours prior to receiving the investigational product. This includes medications that contain naproxen, aspirin, ibuprofen, and other non-steroidal anti-inflammatory drugs. All concomitant medications (e.g., vitamins, antacids, analgesics, prescription medications) taken 28 days prior to vaccination will be recorded in the concomitant medication data collection form. Any medications taken during the 7 days following a dose of vaccine are to be recorded on the participant's memory aid and/or reported to a research team member upon follow up clinic visit. All analgesics and prescription medications from 8 to 28 days post-vaccination will be recorded in the concomitant medication data collection form.

If the investigator learns that the participant has taken a prohibited medication (see inclusion/exclusion criteria) during the time immediately around the dosing of the investigational

product, the investigator will contact the DMID CPM and MO for instructions regarding the participant's continuation in the study.

7 STUDY SCHEDULE

7.1 Screening (Days -7 through -4)

Recruitment: Participants for this study will be recruited from the Mirpur field site. Study staff will visit nearby households of the Mirpur field clinic and have preliminary discussions with adults regarding the study, study procedures, and eligibility. During this process, study staff will identify potential participants for the study and invite them to come to the Mirpur field clinic at a scheduled time for a screening visit.

Research staff will obtain written consent per the standard informed consent process before conducting protocol-specific screening activities.

After signing the ICF, the following screening procedures will be performed:

- Confirm signed informed consent form.
- Collect demographic information, medical history, and concomitant medication history
- Record oral temperature, pulse, and blood pressure
- Perform an abbreviated physical examination, to include: head, eyes, ears, nose, throat (HEENT); lymph nodes; skin; pulmonary; cardiovascular; abdominal; neurological; and musculoskeletal systems
- Review eligibility criteria
- Collect approximately 2 mL of venous blood, for screening labs: complete blood counts (CBC) with differential for WBC, Hg, ANC, platelets count, creatinine, albumin, ALT, serum bilirubin, HBsAg, and HCV antibody
- Collect 13 mL of venous blood for cryopreservation of PBMC, for effector T cell assays
- Collect screening stool for culture and future use.
 - The study staff will provide a stool container to the potential participant and give instructions to collect stool. Participants will bring the stool sample back to the field clinic, within 8 hours of collection, for the completion of the screening stool for culture.
 - 1-2 gm of stool will be frozen at $-80^{\circ}\text{C} \pm 15^{\circ}\text{C}$ for future use microbiome studies

Prospective participants will be carefully screened to ensure that they are in excellent physical and mental health, and that they meet the eligibility criteria. Screening tests will be conducted 4-7 days before Day 1 (the day of first vaccination with dmLT). All women will have a urine pregnancy test performed during screening and a urine pregnancy test on the vaccination days. To be eligible the result of the urine pregnancy test must be negative. During screening, participants will be informed of whether they will be in an oral, sublingual, or intradermal route

of administration cohort so that they are able to anticipate the required duration of fasting necessary prior to vaccination.

7.2 Enrollment/Baseline

7.2.1 VISIT 1- First Vaccination (Day 1)

- Confirm ongoing consent and review eligibility criteria prior to performing any study procedures, to include updating the medical history and concomitant medications
- Record oral temperature, pulse, and blood pressure
- Targeted physical examination, if indicated based on review of medical history
- Urine pregnancy test will be obtained from all women must be negative prior to dosing. Provide instructions to women participants to avoid pregnancy through the 28 days from receipt of the last dose of vaccine.
- Collect approximately 15 mL of venous blood:
 - 3 mL for serum ELISA and neutralization assays
 - 2 mL for ASC assay
 - 2 mL for ALS assay
 - 8 mL for cryopreservation of PBMC, for memory B cell assays
 - Collect plasma from PBMC tubes
- Collect stool (approximately 4 gm) and saliva (approximately 2 mL) for IgA assay.
- 1-2 gm of stool freeze at $-80^{\circ}\text{C} \pm 15^{\circ}\text{C}$ for future use microbiome studies
- Perform Pre-vaccination reactogenicity assessment. Note: the elements of the reactogenicity assessment will vary based on the route of administration of vaccine. The pre-vaccination assessment will serve as the baseline for the comparison of post-vaccination reactogenicity.
- Administer vaccine, per the randomization code and observing the required pre-vaccination fasting for oral and rinsing for SL dosing
- Provide memory aid and other 7-day solicited AE and reactogenicity instructions
- Provide digital thermometer for recording of daily oral temperature for seven days following administration of study product. Participants will be instructed on the use of the digital thermometer.
- Perform post-vaccination reactogenicity assessment. Participants will be examined at the end of a 30 minute observation period following each vaccination for the SL and ID cohorts, and at the end of a 90 minute observation period for oral cohorts.

- Reactogenicity Assessments: Will include brief history for assessment of AE/SAEs just prior to and following vaccination (Days 1, 15, and 29 for oral/SL; Days 1, 22, and 43 for ID), which includes an assessment of systemic and local reactions according to [section 9.1](#).
- Provide stool sample collection container and instructions on how to collect stool sample
- Confirm date and time for Visit 2

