2.1.4 Clinical Experience with Intradermal dmLT

NIAID is sponsoring a Phase 1 dose-escalation study of three sequential ID doses of 0.1, 0.3, 1.0, or 2.0 μ g dmLT, spaced by 21 days (DMID Protocol 13-0013, under IND 16836 NCT02531685). The CVD's Applied Immunology Laboratory is performing all the immunologic assays for this study. DMID 13-0013 trial started in April of 2016 at the CCHMC, and it is the first in human trial with dmLT administered via the ID route. Currently, three doses of 0.1 μ g, 0.3 μ g and 1.0 μ g have been delivered to subjects; no safety signals were seen nor any halting rules were met.

The first generation mLT (LTR192G), which is more toxic in animal (IB V1.0 16 May 2017) than the double-mutant being tested here, was evaluated in a phase 1 trial of ID administered CfaE with or without 100 ng LTR192G. In this study, local reaction at the vaccine injection site were the most common vaccine-related adverse events and were generally mild in severity.

Hypo/hyperpigmentation were observed for 6 months in 45% of the participants and up to 1 year in 18% of the study participants. Preliminary immunogenicity results have revealed robust anti-LTB and anti-CfaE serologic and ASC responses (IgG/IgA), as well as high hemagglutination inhibition titers after ID immunization³⁷.

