7.3.2 VISIT 3 - Second Vaccination (~14 days post dose 1 ±2 days)

- This visit is ~14 days after the first dose for oral and SL cohorts and ~21 days after the first dose for the ID cohorts (window ± 2 days)
- Confirm ongoing consent and review eligibility criteria with the participant prior to performing any study procedures, to include updating the medical history and concomitant medications
- Record oral temperature, pulse, and blood pressure
- Targeted physical examination, if indicated based on review of medical history
- Collect approximately 6 mL of venous blood:
 - 2 mL for serum ELISA and neutralization assays
 - 2 mL for ASC assay
 - 2 mL for ALS assay
- Collect stool (approximately 4 gm) and saliva (approximately 2 mL)
- 1-2 gm of stool frozen at $-80^{\circ}\text{C} \pm 15^{\circ}\text{C}$ for future use microbiome studies
- Urine pregnancy test for all women will be performed and must be negative prior to dosing. Provide instructions to women participants to avoid pregnancy through the 28 days from receipt of the last dose of vaccine.
- Perform pre-vaccination reactogenicity assessment
- Administer vaccine dose 2, per the randomization code and observing the required pre-vaccination fasting for oral and rinsing for SL dosing
- Provide memory aid and other 7-day solicited AE and reactogenicity instructions
- Ask participant if they still have the digital thermometer for recording daily oral temperature for seven days following administration of the study product and offer re-instruction on the use of the thermometer as needed.
- Perform post-vaccination reactogenicity assessment after 90 minutes for oral cohorts and after 30 minutes for SL and ID cohorts. This assessment is to include unsolicited AEs and SAEs.
- Provide stool sample collection container and instructions on how to collect stool sample
- Confirm date and time for Visit 4

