7.3.4 VISIT 5 - Third Vaccination (~14 days post dose-2 ± 2 days)

- This visit is ~14 days after the second dose for oral and SL cohorts and ~21 days after the second dose for the ID cohorts (window ± 2 days)
- Confirm ongoing consent and review eligibility criteria with the participant prior to performing any study procedures, to include updating the medical history and concomitant medications
- Record oral temperature, pulse, and blood pressure
- Targeted physical examination, if indicated based on review of medical history
- Collect approximately 6 mL of venous blood:
 - 2 mL for serum ELISA and neutralization assays
 - 2 mL for ASC assay
 - 2 mL for ALS assay
- Collect stool (approximately 4 gm) and saliva (approximately 2 mL) for IgA assay.

- 1-2 gm of stool frozen at $-80^{\circ}\text{C} \pm 15^{\circ}\text{C}$ for future use microbiome studies
- Urine pregnancy test for women will be performed and must be negative prior to dosing. Provide instructions to women participants to avoid pregnancy through the 28 days from receipt of the last dose of vaccine.
- Perform Pre-vaccination reactogenicity assessment
- Administer vaccine dose 3, per the randomization code and observing the required pre-vaccination fasting for oral and rinsing for SL dosing
- Provide memory aid and other 7-day solicited AE and reactogenicity instructions
- Ask participant if they still have the digital thermometer for recording daily oral temperature for seven days following administration of the study product and offer re-instruction on the use of the thermometer as needed.
- Perform post-vaccination reactogenicity assessment after 90 minutes for oral cohorts and after 30 minutes for SL and ID cohorts. This assessment is to include unsolicited AEs and SAEs.
- Provide stool sample collection container and instructions on how to collect stool sample
- Confirm date and time for Visit 6

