#### 9.3.1. Solicited Events and Symptoms

Solicited adverse events were collected pre-vaccination, 90 minutes post-vaccination following oral dosing or 30 minutes post-vaccination following SL and ID dosing, and then daily for 7 days after each vaccination and graded on a scale of 0 (none), 1 (mild), 2 (moderate) and 3 (severe). Grading scales for solicited adverse events are presented in [Table 7](#). Systemic events for the oral and sublingual routes include: fever, feverishness, fatigue, malaise, myalgia, or headache. Systemic events for the intradermal route include: fever,

feverishness, fatigue, malaise, myalgia, headache, diarrhea, nausea, vomiting, or abdominal discomfort. Local events for the oral route include: irritation of the oral cavity or tongue, diarrhea, nausea, vomiting, and abdominal discomfort. Local events for the sublingual route include: irritation of the oral cavity or tongue, facial nerve disturbance, diarrhea, nausea, vomiting, or abdominal discomfort. Local events for the intradermal route include: injection site pain, redness, swelling, bruising, itching, hypo/hyper pigmentation and induration, vesicles or hardened mass.

The proportion of participants reporting at least one solicited adverse event will be summarized for each solicited adverse event, any systemic symptom, any local symptom, and any symptoms. The 95% CI calculated using Clopper-Pearson methodology from a binomial distribution (SAS Proc Freq with a binomial option) will be presented (beginning at [Table 97](#) and concluding with [Table 104](#)).

For each systemic and local event, any systemic event, any local event, and any solicited event, the maximum severity over 7 days after each vaccination will be summarized for the Safety population. The number and percentage of participants reporting each event will be summarized by the maximum severity and treatment group, separately for each vaccination and over all vaccinations. For each event the denominator is the number of participants with non-missing data for the specific event (beginning at [Table 105](#) and concluding with [Table 112](#)).

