The number of participants reporting a solicited adverse event will be summarized for each day post vaccination for each vaccination and for all vaccinations combined both in a summary table (beginning at [Table 113](#) and concluding with [Table 134](#)) and graphically in a bar chart (beginning at [Figure 238](#) and concluding with [Figure 253](#)). A comparison of the event rate for each treatment group between vaccination 1 and vaccination 2, vaccination 2 and vaccination 3, and vaccination 1 and vaccination 3 will be presented ([Table 135](#), [Table 136](#), and [Table 137](#)).

Solicited adverse events by participant will be presented in Listing [16](#), Listing [17](#), Listing [18](#), Listing [19](#), Listing [20](#), and Listing [21](#).

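### The SAP's incidence, maximum-severity and dose-comparison tables do not use the pre-vaccination reactogenicity baseline, so a Grade 1-2 symptom that merely persists is counted again at the next dose

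*Protocol*

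**What the plan says.** Under Visit 1, Protocol 7.2.1 gives the purpose of the pre-dose examination: "The pre-vaccination assessment will serve as the baseline for the comparison of post-vaccination reactogenicity". The examination is repeated at Visit 3 ("Perform pre-vaccination reactogenicity assessment") and Visit 5 ("Perform Pre-vaccination reactogenicity assessment"), but the sentence about its role as baseline is not.

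SAP 9.3.1 confirms the data exist: "Solicited adverse events were collected pre-vaccination". It then plans four kinds of summary:

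- Incidence with exact intervals (Tables 97-104): "The proportion of participants reporting at least one solicited adverse event will be summarized for each solicited adverse event".
- Worst grade per dose (Tables 105-112): "the maximum severity over 7 days after each vaccination will be summarized for the Safety population".
- Severity by day (Tables 113-134). The Table 113 shell has a Pre-Dose column beside Post-Dose and Days 1-7, and the other tables follow its format for each group and dose.
- Dose against dose (Tables 135-137): "A comparison of the event rate for each treatment group between vaccination 1 and vaccination 2", and likewise for the other two pairs of doses. The shells cross-classify each participant as having no symptoms or mild-or-greater symptoms after each dose.

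Only the third kind shows the pre-dose grade, and only as group counts. Protocol 11.4.2, which the SAP follows, also takes the worst response and splits it into none versus any grade, with no baseline rule.

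**The concern.** The protocol collects a baseline for a stated comparison, and no summary of the primary reactogenicity endpoint makes that comparison within participants. A symptom that began after dose 1, is still there before dose 2 and is reported again afterwards adds one to the dose 2 incidence and to the dose 2 severity distribution. In Table 135 it places the participant among those who reacted to both doses.

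This matters more here than in a trial with a working control arm. SAP 4.2 says the three placebo recipients per cohort are there for blinding, not comparison. The participant's own state just before the dose is then the main means of separating a reaction to that dose from something already present. The group-level Pre-Dose column cannot do this, because it does not show whether the same people had the symptom before and after.

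**Working it through.** **Can carry-over occur under the plan's own rules?**

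- Protocol 5.3.3 allows a later dose while a Grade 1 or 2 AE continues, unless the investigator judges otherwise. An unresolved related Grade 3 AE bars it.
- Any injection-site pigmentation change, even below 1x1 cm, is at least Grade 1 (Protocol Appendix C; SAP Table 7), so persistence alone scores.
- Intradermal doses are 21 days apart (Protocol 7.3.2), and a later dose may go in the same arm (Protocol 6.2.5).
- An earlier intradermal study of a single-mutant LT product found lasting pigmentation: "Hypo/hyperpigmentation were observed for 6 months in 45% of the participants" (Protocol 2.1.4). Protocol 2.1 gives this as 22 subjects, 44.9%.

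**Does another rule remove it?** The AE baseline rule in SAP 3.3 is anchored at screening. The general baseline in the same section is the last value before the first dose. Neither covers a symptom that starts after dose 1.

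**Size.** The plan states no figure for this point. As a check on the interval method, the SAP's exact bound for 0 of 10 is 30.8%, and 1 - 0.025^(1/10) = 30.85%, which agrees. For 0 of 12 the same formula gives 1 - 0.025^(1/12) = 26.5%.

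With n = 12 dmLT recipients per cohort (SAP 4.4.3), one carried-over symptom adds 1/12 = 8.3 percentage points to a symptom row in which that participant has nothing new. Suppose k of the 12 intradermal vaccinees carry pigmentation into dose 2 and none has a new or worse change. The limits are Clopper-Pearson: lower = Beta(0.025; k, 13 - k), upper = Beta(0.975; k + 1, 12 - k).

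| k | Dose 2 row as planned (95% CI) | New-or-worse count (95% CI) |
|---|---|---|
| 2 | 16.7% (2.1-48.4) | 0% (0-26.5) |
| 5 | 41.7% (15.2-72.3) | 0% (0-26.5) |
| 6 | 50.0% (21.1-78.9) | 0% (0-26.5) |

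The value k = 5 lies near 12 x 0.449 = 5.4. That rate is for another product at six months, so a range is shown.

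**Effect on Table 135.** Take k = 5, all five first reported within 7 days of dose 1, and no other local symptom. The local-symptom panel shows 5 in the yes/yes cell, 7 in no/no and none elsewhere. On a new-or-worse basis the same five move to dose 1 yes, dose 2 no. The planned table reads as five repeat reactions, whereas the flagged table shows none.

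**What is little affected.** The Post Any Dose column counts each participant once, so a reaction already counted after an earlier dose adds nothing. It can be raised only by a symptom present before dose 1 or one starting between Day 8 and the next dose. Halting on solicited events needs Grade 3, and 5.3.3 confines carry-over mainly to Grades 1-2. Cohort E received only two doses and no later intradermal cohort enrolled (SAP 4.1), so intradermal skin carry-over can arise only at its dose 2.

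**The case against.** The other side has a fair case. The endpoint is the occurrence of events through 7 days after each dose, not their onset. All-grade counting is a conservative Phase 1 choice, it follows Protocol 11.4.2, and no hypothesis is tested. Listings 16-21 give solicited events by participant. Conduct rules also limit carry-over: Protocol 5.3.3 defers a later dose while symptoms would blur the assessment, eligibility is reviewed again at Visits 3 and 5, recent gastrointestinal symptoms are an exclusion, and Protocol 6.2.5 steers the injector away from marks that would obscure the site. A new-or-worse flag can also hide something real: a fresh reaction at a new site with the same grade as an old mark would not be flagged.

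Most of this stands as a limit on size. It does not supply the missing rule, because continuing Grade 1-2 events remain permitted and no planned table separates them within participants. The last point is a reason to keep the all-grade counts beside the flag.

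A reader might infer more than the documents support:

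- *That the SAP ignores the pre-dose data.* It does not, since Tables 113-134 display them by dose.
- *That the SAP calls persisting symptoms new reactions.* It does not say so. The double count follows from the absence of a rule.
- *That reactogenicity would appear to build up over doses.* Pure carry-over gives a flat pattern, as the k = 5 example shows. A rise would need onset after Day 7 or reactions in other participants.
- *That about 45% of intradermal dmLT recipients should be expected to carry pigmentation forward.* That figure comes from a different LT product six months after the first dose. For intradermal dmLT, the protocol reports no safety signal at the doses given so far.

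**Conclusion.** The point holds as a gap in the analysis rules, of minor weight. The pre-vaccination assessment is named as the reactogenicity baseline and shown by group, but it is not used in the incidence, maximum-severity or dose-comparison tables. The bias is confined to the per-dose columns and to Tables 135-137, mainly at Grades 1-2.

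The 16.7% to 50.0% range is an illustration, not a forecast. It rests on three assumptions: 2 to 6 of 12 vaccinees carry a change forward, they report it again after dose 2, and nothing new occurs. The documents do not say how site staff record a persisting symptom, so the true size is unknown until the pre-dose grades are set against the post-dose grades for each participant.

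The documents also leave open which assessment is the baseline for doses 2 and 3, because the defining sentence stands only under Visit 1.

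**What to change.** In SAP 9.3.1:

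1. State that the reactogenicity baseline for each dose is that dose's own pre-vaccination assessment.
2. Derive a flag for each solicited symptom and dose, set when the maximum post-dose grade exceeds the pre-dose grade.
3. Show the flagged count beside the all-grade count in Tables 97-112.
4. Present Tables 135-137 on both bases.

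The cost is one derived variable and additional columns, from data already collected. The flag misses a new reaction of the same grade at a new site, so the all-grade version must be kept and that limitation footnoted.
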